Statistical Analysis Plan (Short)

Comparative effect of two educational videos for people with knee osteoarthritis (vidEO): An online randomised controlled trial

Version: 2

Author/s of SAP: [name] and [name] (Biostatisticians, Centre for Epidemiology and Biostatistics), University of Melbourne
[name], CHESM, University of Melbourne

Date of SAP: 14/12/2021

Author/s of template: [name] (Deputy Head MISCH Biostatistics), University of Melbourne (Template adapted from www.pfizer.com)

Date of template: 25/10/2021

[figure not shown]
Table of Contents

1 Introduction	3
2 Data Source	4
3 Analysis Objectives.....	5
3.1 Aim 1	5
3.2 Aim 2	5
3.3 Aim 3	5
4 Analysis sets/Populations/Subgroups.....	5
5 Endpoints and Covariates	6
6 Handling of Missing Values and Other Data Conventions	6
7 Statistical Methodology	7
7.1 Statistical Procedures.....	7
7.1.1 Aim 1	7
7.1.2 Aim 2	7
7.1.3 Aim 3	Error! Bookmark not defined.
7.2 Measures to Adjust for Multiplicity, Confounders, Heterogeneity	8
8 Sensitivity Analyses	8
9 QC Plans	8
10 Programming Plans	8
11 References	8
Appendix 1	9
Appendix 2	16
Appendix 3	18

1 Introduction

Objectives	To determine if an educational video based on an empowerment and participatory discourse improves self-efficacy to manage knee OA pain and reduced fear of movement more than an educational video based on a disease information and impairment discourse, among people with knee osteoarthritis symptoms.
Study Design	Two-arm, parallel groups superiority randomised controlled trial
Planned Sample Size	516
Study Procedures	Our trial will be delivered via an online survey (Qualtrics, Provo, UT, USA) and Vimeo (Vimeo Inc, NYC, USA) video sharing platform. Volunteers will be recruited by a digital survey-based research company (Cint PTY LTD) and complete an online screening survey. Eligible participants will then be invited to read the information sheet and digitally consent to participate in the study. They will provide demographic information and answer the baseline questionnaires. They will then be randomised to one of two intervention groups. On the next page of the survey they will be presented with a video to watch before moving on the post-intervention questionnaire.
Duration of the study	Anticipated participant recruitment start: November 2021 Anticipated data collection end: December 2021 Recruitment for this study is anticipated to take approximately 3-4 weeks.

Figure 1. Study chart

2 Data Source

Participant recruitment will be managed by an external company, Cint PTY LTD. Data security will be managed according to their data privacy and security protocols.

Data collection will be managed wholly online through Qualtrics, an electronic data capture system. Qualtrics is a secure web application for building and managing research questionnaires and databases. The University of Melbourne holds a licence for staff use of Qualtrics and surveys and associated data will only be accessible via secure login by the study research staff.

Re-identifiable/coded data

Questionnaires will be completed electronically and anonymously, with no identifying information being recorded. Electronic data will be stored in the Qualtrics website, accessible only to the study research staff by password protection. Data from within Qualtrics will eventually be exported to Microsoft Excel and other statistical packages used by the researchers for analyses and stored securely on password-protected servers accessible only to the study research staff.

3 Analysis Objectives

The aim of this randomised controlled trial (RCT) is to compare the effect of two knee OA educational videos on people with knee OA.

3.1 Aim 1

The primary hypotheses are that a knee OA educational video based on an empowerment discourse and emphasising participation in effective lifestyle behaviours will lead to 1) feeling more confident to self-manage knee OA pain, and 2) having less fear of movement, compared to an educational video based on a disease information and impairment discourse.

3.2 Aim 2

We secondarily hypothesise that after watching the novel educational video, people with knee OA will have reduced levels of concern, more positive expectations about their knee OA prognosis and the benefit to be gained from physical activity, will be more motivated to be physically active, and will have at least as accurate beliefs about knee OA disease.

3.3 Aim 3

N/A

4 Analysis sets/Populations/Subgroups

Participants will be eligible if they: i) live in Australia; ii) are aged 45 years or over; iii) have experienced activity-related knee pain during the past 3 months or have been told by a health professional that they have knee OA, iv) have not had a hip or knee joint replacement; v) are not scheduled/referred to see an orthopaedic surgeon or are already on a waiting list for hip or knee joint replacement; vi) do not knowingly have any type of systemic arthritis (e.g. rheumatoid arthritis, gout), or have morning stiffness that lasts longer than 30 minutes; vii) do not have a health condition that makes them unable

to walk; viii) have not seen a health professional for their knee pain during the previous three months; and ix) are able to easily understand verbal and written English language.

5 Endpoints and Covariates

All variables are listed in Appendix 1 and the coding of the derived variables can be found in Appendix 2.

5.1 Primary Outcomes

- Change in Arthritis Self Efficacy Scale – Pain Subscale (post-intervention minus baseline),
- Change in Brief Fear of Movement Scale for Osteoarthritis (baseline minus post-intervention).

5.2 Secondary Outcomes

- Level of Concern (ordinal, range 0=Not at all concerned – 4=Extremely concerned, measured at baseline and post-intervention)
- Change in Credibility/expectation questionnaire – Part 1 (post-intervention minus baseline)
- Change in Credibility/expectation questionnaire – Part 2 (post-intervention minus baseline)
- Change in Importance of physical activity (post-intervention minus baseline)
- Change in Motivation to be physically active (post-intervention minus baseline)
- Change in Knee osteoarthritis knowledge scale (post-intervention minus baseline)
- Perceived likelihood of needing surgery (ordinal, measured at baseline and post-intervention)
- Perceived change in hope (binary, only measured at post-intervention)
- Satisfaction with meeting information needs (ordinal, only measured at post-intervention)

6 Handling of Missing Values and Other Data Conventions

An appendix table will provide summaries of baseline characteristics and baseline levels of primary and secondary outcomes where measured between two groups: those participants who provide both primary outcomes post-intervention, and those participants who are missing either or both primary outcomes. If less than 5% of both primary outcomes is missing, analyses will be performed on complete case data (Lawford et al, Under review; Sharma et al., 2021). If greater than 5% of either primary outcome is missing, multiple imputation will be applied for the primary analysis. Missing outcomes will be imputed using chained equations with predictive mean matching and five nearest neighbours for continuous outcomes. Imputation models for continuous outcomes post-intervention will include all primary and secondary outcomes at both baseline and post-intervention,

along with age, gender, BMI, education level, geographical location, employment status, duration of symptoms, ethnicity, personal relevance and pain during walking. Data will be imputed for each treatment group separately. The number of imputed data sets created will be based on the percentage of patients in the sample with missing outcome data (e.g., 15 imputed datasets if 15% of participants have missing data). Estimates from the imputed datasets will be combined using Rubin's rules. (Carpenter JG, Kenward MG. Multiple imputation and its application. West Sussex, UK: John Wiley & Sons Ltd; 2013.)

7 Statistical Methodology

7.1 Statistical Procedures

A biostatistician ([name], supervised by [name]) will analyse de-identified data in Stata version 16.1 (StataCorp LLC, College Station, TX, USA), while blind to group allocation. Descriptive data will be presented by intervention group as mean (SD), median (IQR) or n (%) as appropriate. Comparative analyses between groups will be performed using intention-to-treat according to the group to which the participant was randomised, irrespective of whether they adhered to the intervention. The number included in each analysis will be reported. Standard diagnostic plots will be used to check model assumptions, including assessing linearity and homoscedasticity, where appropriate.

7.1.1 Aim 1

Separate linear regression models for each primary outcome will be used to estimate the between-group mean (95% CI) difference in change scores (either baseline minus post-intervention or post-intervention minus baseline, so that positive values favour the experimental group (allocated the 'empowerment and participatory discourse' video), adjusted for the outcome at baseline. Post-intervention time point was 'immediately following watching the video'.

7.1.2 Aim 2

Separate linear regression models for each continuous secondary outcome will be used to estimate the between-group mean (95% CI) difference in change scores (post-intervention minus baseline, so that positive values favour the experimental 'empowerment and participatory discourse' group), adjusted for the outcome at baseline. For the binary secondary outcome, perceived change, groups will be compared using logistic regression, with results reported as risk differences and risk ratios, with corresponding 95% CIs. For ordinal secondary outcomes, ordinal logistic regression models will be fitted similarly, adjusted for the outcome at baseline where able. The proportional odds

assumption will be assessed using the Brant test. If proportional odds cannot be assumed, multinomial regression models will be fitted. Results will be reported as odds ratios, or relative risk ratios if multinomial regression is used, with corresponding 95% CIs.

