7.2 Measures to Adjust for Multiplicity, Confounders, Heterogeneity

We have two primary outcomes and so have adjusted the alpha for each primary outcome to 0.025 to give an overall alpha of 0.05 across both outcomes. We have several secondary outcomes. All secondary outcomes are exploratory and not powered for. We will therefore not adjust for multiple secondary outcomes but instead report all effect sizes, confidence intervals, and p values in order to let readers use their own judgment about the relative weight of the conclusions. This approach aligns with the usage of p-values favoured by the American Statistical Association. [Wasserstein RL, Schirm AL, Lazar NA. Moving to a world beyond “ $p < 0.05$ ”. *The American Statistician*. 2019; 73:1-19.]

8 Sensitivity Analyses

If multiple imputation is used for the primary outcomes, sensitivity analyses will be conducted on complete case analysis.

9 QC Plans

Data quality will be checked/promoted through a process of identifying extreme values and checking the source of these values in case of a data entry error. A record of any/all manual corrections to data will be maintained. Calculations of scores from multi-item scales will be carried out using Microsoft Excel functions and cross-checked using other statistical packages to reduce errors.

10 Programming Plans

A list of all tables, figures, listings and their templates can be found in Appendix 3.

11 References

vidEO study project proposal - V3

References as detailed or as per vidEO study project proposal - V3.

Appendix 1

VARIABLES IN THE DATA SET

Domain	Label	Measurement method	Details
Age	AGE	Calculated from date of birth	Reported in years
Gender	GENDER	Self-reported using the following categories: 
 – Male = 1 – Female = 2 – Other (please specify) / Prefer not to say = 3 – Non-binary = 4 	Number and proportion of participants responding to each category will be reported.
State/territory	STATE	Self-reported using the following categories: ACT, NSW, NT, QLD, SA, TAS, VIC, WA	N (%) in each category
Geographical location	LOCATION	Determined from self-reported residential postcode and classified according to the Australian Standard Geographical Classification (ASGC Remoteness Structure)	N (%) in each category of: major city, inner regional, outer regional, remote and very remote locations
Height	HEIGHT	Self-reported	Reported in metres
Weight	WEIGHT	Self-reported	Reported in kilograms

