Part 1, range 3-27								
Part 2, range 2-18								
Importance of physical activity, range 1-5								
Motivation to be physically active, range 0-10								
Knee Osteoarthritis Knowledge Scale, range 11-55								
	Baseline, counts (proportions)		Post-intervention, counts (proportions)		Between-group (n=xxx)			

	Group 1 (n=xxx)	Group 2 (n=xxx)	Group 1 (n=xxx)	Group 2 (n=xxx)	Relative risk ^c [95% CI]	P-value	Risk difference ^d [95% CI]	P- value
Perceived change to more hopeful ^e	n/a	n/a						
	Baseline, counts (proportions)		Post-intervention, counts (proportions)		Between-group (n=xxx)			
	Group 1 (n=xxx)	Group 2 (n=xxx)	Group 1 (n=xxx)	Group 2 (n=xxx)	Odds ratio ^f [95% CI]	P-value	Relative risk ratio ^g [95% CI]	P- value
Level of concern ^h					OR [95% CI]	P	–	–
0=Not at all concerned					–	–	REFERENCE	–
1=A little concerned					–	–	RRR [95% CI]	P
2=Quite concerned					–	–	RRR [95% CI]	P
3=Very concerned					–	–	RRR [95% CI]	P
4=Extremely concerned					–	–	RRR [95% CI]	P
Perceived personal likelihood of ever needing knee replacement surgery					OR [95% CI]	P	–	–

1 = very unlikely to need surgery				–	–	REFERENCE	–
2 = unlikely to need surgery				–	–	RRR [95% CI]	P
3 = neutral				–	–	RRR [95% CI]	P
4 = likely to need surgery				–	–	RRR [95% CI]	P
5 = very likely to need surgery				–	–	RRR [95% CI]	P
Satisfaction that video met information needs				OR [95% CI]	P	–	–
1 = very unsatisfied	n/a	n/a		–	–	REFERENCE	–
2 = moderately unsatisfied	n/a	n/a		–	–	RRR [95% CI]	P
3 = neutral	n/a	n/a		–	–	RRR [95% CI]	P
4 = moderately satisfied	n/a	n/a		–	–	RRR [95% CI]	P
5 = very satisfied	n/a	n/a		–	–	RRR [95% CI]	P

^a Within-group change was calculated as post-intervention minus baseline for all continuous outcomes, except Brief Fear of Movement Scale for Osteoarthritis where the within-group change was calculated as baseline minus post-intervention, so that positive values indicate improvement.

^b Positive values favour Group 2. Mean (95% CI) difference in change between groups, adjusted for the outcome at baseline, estimated using separate regression models for each outcome.

^c Relative risks > 1 favour Group 2.

^d Risk differences > 0 favour Group 2.

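### The two primary outcomes are tested at alpha 0.025 each but reported with 95% confidence intervals, so interval and planned test can disagree when p lies between 0.025 and 0.05

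*SAP*

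**What the plan says.** The SAP has two primary outcomes: change in the pain subscale of the Arthritis Self-Efficacy Scale (ASES-Pain) and change in the Brief Fear of Movement Scale (BFMS).

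- **Test level.** Section 7.2 says the authors "have adjusted the alpha for each primary outcome to 0.025 to give an overall alpha of 0.05 across both outcomes". The secondary outcomes are called exploratory and are left unadjusted.
- **Interval, text.** Section 7.1.1 reads "Separate linear regression models for each primary outcome will be used to estimate the between-group mean (95% CI) difference in change scores".
- **Interval, table shell.** In Table 2, ASES and BFMS share one column of mean differences with 95% intervals with the continuous secondary outcomes, next to a P-value column. Footnote b applies to all of them: "Mean (95% CI) difference in change between groups, adjusted for the outcome at baseline, estimated using separate regression models for each outcome".
- **Sidedness.** The Introduction describes a "Two-arm, parallel groups superiority randomised controlled trial". No section says whether the tests are one-sided or two-sided.

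The SAP nowhere mentions a 97.5% interval, says that the primary 95% intervals are unadjusted for multiplicity, or repeats the 0.025 threshold in the Table 2 footnotes.

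**The concern.** A 95% confidence interval corresponds to a two-sided test at 0.05. The plan tests each primary outcome at 0.025, so the interval shown for the main results belongs to a different, more lenient test from the one planned. Between the two thresholds they disagree: the interval excludes zero and the planned test does not reach its level.

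Many readers judge a result by whether the interval covers zero. For the two primary hypotheses, that habit would bypass the only multiplicity control in the SAP. The table layout makes this easier, because primaries with a split alpha and secondaries with none appear in one format and nothing on the page tells them apart.

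**Working it through.** **Inputs.** Alpha of 0.025 per primary outcome, overall alpha of 0.05 and two primary outcomes (section 7.2); 95% intervals (section 7.1.1, Table 2); planned sample size 516 (Introduction), used only for degrees of freedom. Assumption: two-sided tests.

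**1. The plan's own figure.** 0.025 + 0.025 = 0.05, as stated. For independent tests the exact familywise error is 1 − (1 − 0.025)² = 0.0494. The alpha split is correct.

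**2. Critical values.**
- 95% interval: z(0.975) = 1.960, so estimate ± 1.960 SE.
- Two-sided test at 0.025: z(0.9875) = 2.241, so the matching interval is estimate ± 2.241 SE, which is a 97.5% CI.
- Ratio: 2.241 / 1.960 = 1.144, so the 97.5% interval is about 14% wider. Equivalently, the 95% interval is 1 − 1.960 / 2.241 = 12.6% narrower than the one that matches the test.
- Check with the t distribution on 516 − 3 = 513 degrees of freedom (intercept, group, baseline score): 1.965 and 2.248, ratio 1.144.

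**3. Where interval and test disagree.** They disagree when 1.960 < |z| < 2.241, that is, when p lies between 0.025 and 0.05. Example with z = 2.10:

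| Quantity | Result |
|---|---|
| p-value | 0.036 (above 0.025) |
| Lower limit, 95% CI | 2.10 − 1.960 = +0.14 SE (excludes zero) |
| Lower limit, 97.5% CI | 2.10 − 2.241 = −0.14 SE (includes zero) |

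**4. How often.** Under the null, the chance per outcome is 0.05 − 0.025 = 2.5%. If the true effect gives power P at alpha 0.025, the expected z is 2.241 + z(P), and the chance is the power at 0.05 minus the power at 0.025. The SAP states no power, so P is assumed:

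| Assumed power at 0.025 | Power at 0.05 | Chance of disagreement |
|---|---|---|
| 50% | 61.1% | 11.1% |
| 80% | 86.9% | 6.9% |
| 90% | 94.1% | 4.1% |

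**5. If a reader uses the intervals as the test.** Calling the trial positive when either 95% interval excludes zero has a familywise error of 1 − 0.95² = 0.0975 if the two estimates are independent. At an assumed correlation of 0.7 the chance that both intervals cover is 0.9165, so the error is 1 − 0.9165 = 0.0835. Both figures exceed the planned 0.05. They describe a misreading that the table layout invites. They are not the error rate of the planned test.

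**The case against.** The best defence is that the decision rule is intact. Multiplicity is controlled through alpha, Table 2 prints a p-value for each primary outcome, and nothing in the SAP makes exclusion of zero the criterion for success. Section 7.1.1 uses the interval for estimation, and a 95% interval has its nominal coverage for its own parameter. All of this stands, and it limits the weight of the point. It does not remove the mismatch: the table shell does not state 0.025, and in the zone above the interval would still point the other way from the p-value beside it.

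A second defence is that one-sided tests at 0.025 would match a two-sided 95% interval exactly. That is correct arithmetic, and the primary hypotheses are directional. But the SAP does not say the tests are one-sided, and two-sided is the usual default.

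Two stronger readings are tempting, and the document supports neither. A reader might infer that the trial does not hold its overall type I error; it does, because the planned tests at 0.025 sum to 0.05. A reader might also object that two 95% intervals have joint coverage below 95% (0.9025 if independent). The figure is right, but section 7.2 promises only "to give an overall alpha of 0.05 across both outcomes". It makes no claim of simultaneous coverage, so failing to provide it is not an error against the plan.

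**Conclusion.** The point holds as a moderate mismatch between the reported interval and the decision rule for the two primary outcomes. It rests on two-sided testing, which is an assumption. The size is a factor of 1.144 in interval width, and the message changes only if a primary p-value falls between 0.025 and 0.05. The chance of that is 2.5% per outcome under the null and about 4% to 11% over the assumed range of power. Point estimates, standard errors, p-values, models and the alpha split are unaffected. It does not invalidate the analysis, but it is worth correcting before results are seen because the change is so small.

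**What to change.** - In section 7.1.1 and Table 2 (column header and footnote b), report 97.5% confidence intervals for ASES-Pain and BFMS. The 95% intervals may stand beside them if labelled as unadjusted for multiplicity.
- Add to the Table 2 footnote that the primary outcomes are judged at p < 0.025, and state in section 7.2 whether the tests are two-sided.
- Keep 95% intervals for the exploratory secondary outcomes.

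A lighter alternative is to keep only the 95% intervals and add a sentence saying that they are unadjusted and that the primaries are judged at p < 0.025. That removes the ambiguity, but the displayed interval would still differ from the test, so the 97.5% interval is the better choice.

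The cost is a few words in the SAP and table shell, with no new data or models. The downside is that the primary intervals become about 14% wider.

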^e Logistic regression model fitted, unadjusted.

^f Ordinal logistic regression models fitted, adjusted for the outcome at baseline where able, as proportional odds could be assumed. Odds ratios > 1 favour Group 2.

^g Multinomial regression models fitted, adjusted for the outcome at baseline where able, as proportional odds could not be assumed. Relative risk ratios > 1 favour Group 2.

^h Question asked “How concerned are you about your knee problem?”

SD = standard deviation.

ASES = Arthritis Self-efficacy Scale (Pain subscale); scored 0-10, with higher scores indicating greater self-efficacy.

BFMS= Brief Fear of Movement Scale for Osteoarthritis; scored 6-24, with higher scores indicating greater fear.

Appendix 1. Baseline characteristics and outcome summary measures of participants who did and did not complete both primary outcomes, reported as mean (standard deviation) unless otherwise stated.

Domain	Units / categories	Completed both primary outcomes [N = xxx]	Incomplete one or both primary outcomes [N = xxx]
Age	Years		
Gender, n (%)	Male		
	Female		
	Non-binary		
	Other (please specify)		
	Prefer not to say		
State/territory, n (%)	Australian Capital Territory		
	New South Wales		
	Northern Territory		
	Queensland		
	South Australia		
	Tasmania		
	Victoria		
	Western Australia		
Geographical location ^a , n (%)	Major city		
	Inner regional		
	Outer regional		
	Remote		
	Very remote		
Height	Metres		
Weight	Kilograms		
Body mass index	kg/m ²		
Level of education, n (%)	<3 years of secondary education (high school)		
	3 or more years of secondary education (high school)		
	Some education beyond high school e.g., trade/technical/vocational training		

	Completed tertiary education (college or university)
Current employment situation, n (%)	Unemployed/not employed/ e.g., full-time carer, full-time student
	Retired (not due to health reasons)
	Unable to work due to health reasons
	Paid work part time
	Paid work full time
Ethnicity, n (%)	Australian/New Zealand
	Aboriginal and Torres Strait Islander
	European
	Asian
	Other Oceania
	North African & Middle Eastern
	Sub-Saharan Africa
	North American
	South American
	Other
Pain severity during walking ^b	0-10
Pain duration, n (%)	Less than one year
	One to two years
	Two to five years
	Five to ten years
	Ten to fifteen years
	Fifteen to twenty years
	More than twenty years
Where received OA information ^c , n (%)	No information received
	GP or family doctor
	Orthopaedic surgeon

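### For the three ordinal secondary outcomes, a failed Brant test leaves four category-wise relative risk ratios against the lowest category and no overall treatment estimate or test

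*SAP*

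**What the plan says.** Section 7.1.2 states the first-choice model: "For ordinal secondary outcomes, ordinal logistic regression models will be fitted similarly, adjusted for the outcome at baseline where able". On the check of proportionality, it says only that this "assumption will be assessed using the Brant test", with no significance level and no statement of which Brant result (overall or per term) counts. The fallback is: "If proportional odds cannot be assumed, multinomial regression models will be fitted". The two reports are alternatives: "Results will be reported as odds ratios, or relative risk ratios if multinomial regression is used, with corresponding 95% CIs".

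The Table 2 shell (Appendix 3) fills in the detail. For each five-level outcome the lowest level is marked as the reference: "0=Not at all concerned" for concern, "1 = very unlikely to need surgery" for surgery and "1 = very unsatisfied" for satisfaction. The other four levels each have their own RRR and P value. The outcome-level row holds only the OR and its P value; its RRR and P cells are dashes. Footnote g reads: "Multinomial regression models fitted, adjusted for the outcome at baseline where able, as proportional odds could not be assumed".

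Sections 7.1.2, 7.2 and 8 and the table footnotes name no joint test and no summary estimate under the fallback. Section 7.2 classes all secondary outcomes as exploratory and unpowered. It promises effect sizes, confidence intervals and P values without multiplicity adjustment.

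**The concern.** Aim 2 (section 3.2) is directional; one part of it is that concern falls. A multinomial model ignores category order. If the Brant test fails, the reader gets four contrasts sharing one reference cell, and no single figure for whether responses moved in the hypothesised direction. Section 7.2 relies on effect sizes and intervals for interpretation, and four correlated ratios serve that purpose poorly.

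Two features add to this. First, the reference is fixed at an end of the scale, so all four ratios are imprecise together if few people choose it. Second, the trigger is undefined. Concern and surgery are adjusted for their baseline value, so an overall Brant test can fail because of the baseline term while the treatment effect is proportional. A usable treatment OR would then be discarded because of a nuisance term. Satisfaction has no baseline measure, so this second feature does not apply to it.

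**Working it through.** The SAP gives no figure to reproduce on this point. The checks below use its sample size and assumed category shares.

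**Inputs.** N = 516 (section 1). The allocation ratio is not stated; 1:1 is assumed, so n = 258 per arm. There are five levels per outcome, with the lowest as reference (Table 2 shell). Category shares are assumptions. No baseline covariate is included in steps 1 to 3.

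**1. Precision.** With equal shares in both arms:

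- SE(log RRR for level j) = sqrt(2/(n·p_ref) + 2/(n·p_j))
- SE(common log OR) = sqrt(12/(N·(1 − Σp³)))
- 95% CI factor either way = exp(1.96·SE)

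Example, shares 2/6/22/40/30%:

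- level 2: sqrt(2/5.16 + 2/15.48) = 0.72
- level 4: sqrt(2/5.16 + 2/103.2) = 0.64
- common log OR: Σp³ = 0.102, so sqrt(12/(516 × 0.898)) = 0.161

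| Assumed shares, lowest to highest (%) | Reference, people per arm | SE log RRR | CI factor | SE common log OR |
|---|---|---|---|---|
| 1/4/20/40/35 | 2.6 | 0.89–0.98 | 5.7–6.9 | 0.162 |
| 2/6/22/40/30 | 5.2 | 0.64–0.72 | 3.5–4.1 | 0.161 |
| 5/15/30/30/20 | 12.9 | 0.43–0.45 | 2.3–2.4 | 0.158 |
| 10/25/30/20/15 | 25.8 | 0.32–0.36 | 1.9–2.0 | 0.157 |
| 20/20/20/20/20 | 51.6 | 0.28 | 1.7 | 0.156 |

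The CI factor for the common OR is 1.36 to 1.37 throughout. The two quantities are not on the same footing: under proportional odds the RRR for the top category is larger than the OR (2.04 to 2.18 when the OR is 1.57). The SE ratio alone therefore overstates the loss for that contrast.

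**2. Empty reference cell.** At 2% in both arms, the chance that at least one arm has nobody in the reference category is 1 − (1 − 0.98^258)² = 1.1%. With 2% in one arm and an OR of 1.5, the other arm has 1.34%, and the chance is about 0.5% + 3.1% = 3.6%. At 1% in both arms it is 14%. From 5% upwards it is negligible.

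**3. Power.** Simulation with 10,000 trials per scenario and a true common OR of 1.57:

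- one-df proportional-odds test: 78% to 82%
- four-df multinomial treatment test: 59% to 62%
- best single RRR: 1%, 11%, 35%, 55% and 71% at reference shares of 1%, 2%, 5%, 10% and 20%

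These apply where proportional odds holds, so the switch should be rare. With shares 3/7/25/40/25% and an OR of 1.5, a Brant-type test at an assumed 0.05 switched in about 3% of trials. Counting every switched trial as no result lowered power only from 70% to 68%. Under one assumed non-proportional pattern (3/7/25/40/25% against 6/10/12/32/40%) the switch occurred in 98% of trials. The ranking then reversed: 99.7% power for the four-df test against 70% for the ordinal test.

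**4. Trigger.** Simulation for a baseline-adjusted outcome (516 people, treatment exactly proportional with OR 1.5, linear baseline term, 800 runs, tests at an assumed 0.05):

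- Baseline slopes running from 0.7 to 1.3 across cut-points: the overall Brant test rejected in 61% of trials, the treatment term in 6%.
- Slopes from 0.8 to 1.2: 26% against 6%.
- Fully proportional data: 4% to 7%.
- 30% to 50% of people repeating their baseline answer, with no treatment effect: 6% to 8%.

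So the choice between overall and treatment-term result can matter a great deal, but only if the baseline effect varies across cut-points.

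**The case against.** The fallback is prespecified and multinomial regression is a valid model when proportional odds fails. The outcomes are exploratory, the primary analyses are untouched, and Table 2 prints counts and proportions for every category by arm, so a real shift would be visible. All of this stands, and it keeps the point minor. It does not supply the missing summary or joint test.

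Two stronger readings are tempting and are not supported.

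- A reader might infer that the RRRs will be unstable. That depends on how many people choose the lowest category, and the SAP gives no shares. At 10% to 20% the ratios are estimable. That the lowest satisfaction level will be rare is conjecture.
- A reader might infer that the fallback costs power. The gap in step 3 arises under proportional odds, where the switch is seldom made, and it reverses under the one non-proportional pattern tried. The SAP does not plan the four-df test that had the high power, so its readers would not see that benefit either.

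On the trigger, the SAP does not say that the overall result decides, and Brant results can also be read term by term. This is an ambiguity to close, not a stated error.

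**Conclusion.** The structural point holds on the SAP's own text. After a failed Brant test, each of the three ordinal outcomes would be reported as four RRRs against the lowest category, with the ordering dropped and no overall treatment estimate or test. Each RRR is less precise than the common OR at every share examined, with an SE about 1.8 times as large at a 20% reference share (0.28/0.156) and 4.0 to 4.5 times at 2% (0.64/0.161 to 0.72/0.161). The size rests on assumed shares, 1:1 allocation and no baseline adjustment. The trigger is undefined; for concern and surgery the baseline term alone could cause the switch. No power loss is established where odds are truly non-proportional. Severity is minor, limited to exploratory secondary outcomes.

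**What to change.** In section 7.1.2 and the Table 2 shell:

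- Report the common OR with a robust SE as the summary treatment effect for each ordinal outcome whatever the Brant result, baseline-adjusted for concern and surgery.
- Assess proportionality term by term and state the level used. If a term fails, free only that term in a partial proportional-odds model, and show the treatment ORs at each cumulative split as a supplement.
- If the multinomial model is kept as a supplement, add its joint four-df treatment test and choose a well-populated reference category.

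If the RRR columns stay, footnote g also needs checking. It says ratios above 1 favour Group 2, but for concern and surgery Appendix 2 marks lower as better and the reference is the best category. A Group 2 to Group 1 ratio above 1 would then favour Group 1.

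The cost is SAP wording, table-shell edits and one supplementary model. The downside is that, when the treatment effect is not proportional, the common OR is an average over cut-points; the supplement shows what it averages.
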